8.4.2.2 Secondary Endpoint Methods

PFS and OS will be summarized descriptively using Kaplan-Meier methodology. Median values of PFS and OS, along with two-sided 95% CIs using the Brookmeyer and Crowley method, will be calculated for each cohort. PFS rates at 6 and 12 months, and OS rates at 12 and 24 months will also be estimated. Associated two-sided 95% CIs will be calculated using the Greenwood formula. Additional survival analysis may be conducted for up to 5 years beyond analysis of the primary endpoint.

[REDACTED]

8.4.3 Safety Analyses

Safety analyses will be performed in all treated subjects. Descriptive statistics of safety will be presented using National Cancer Institute (NCI) Common Terminology Criteria for Adverse Events (CTCAE) version 4.0. All on-study AEs, Grade 3-4 AEs, treatment-related AEs, Grade 3-4 treatment-related AEs, SAEs, treatment-related SAEs, and AEs leading to discontinuation will be tabulated using worst grade per NCI CTCAE v 4.0 criteria by system organ class and preferred term. On-study lab parameters including hematology, chemistry, liver function, and renal function and Grade 3-4 Lab Abnormalities will be summarized using worst grade NCI CTCAE v 4.0 criteria.

8.4.4 Pharmacokinetic Analyses

The nivolumab and ipilimumab concentration data obtained in this study may be combined with data from other studies in the clinical development program to develop or refine a population PK model. This model will be used to evaluate the effects of intrinsic and extrinsic covariates on the PK of nivolumab and ipilimumab and to determine measures of individual exposure (such as steady-state peak, trough, and time-averaged concentration). In addition, model determined exposures may be used for exposure-response analyses. Results of population PK and exposure response-analyses will be reported separately.

[REDACTED]

8.4.6 Outcomes Research Analyses

Subject's overall health state on a visual analog scale (EQ-VAS) at each assessment time point will be summarized using descriptive statistics by treatment arm (N and N-I), as randomized or assigned.

Proportion of subjects reporting problems for the 5 EQ-5D dimensions at each assessment time point will be summarized by level of problem and by treatment group, as randomized or assigned. Percentages will be based on number subjects assessed at assessment time point.

A by-subject listing of EQ-5D with the problem levels for each of the 5 dimensions (mobility, self-care, usual activities, pain/discomfort and anxiety/depression), health state (5 dimensions digits combined in a 5-digit number) and EQ-VAS will be provided.

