Subjects to be enrolled in the SCLC expansion cohort will be randomized in a 3:2 ratio to one of 2 expansion groups: Arm A (150 subjects, nivolumab 3 mg/kg every 2 weeks (Q2W) or Arm B (100 subjects, nivolumab 1 mg/kg + ipilimumab 3 mg/kg every 3 weeks (Q3W) for 4 cycles

followed by nivolumab 3 mg/kg Q2W) and will be stratified for number of prior treatment lines (1 vs 2 prior chemotherapy regimens).

Subjects to be enrolled in the OC expansion cohort will be randomized in a 1:1:1 ratio to one of 3 dose level groups:

- Arm A (40 subjects, nivolumab 1 mg/kg + ipilimumab 3 mg/kg every 3 weeks (Q3W) for 4 cycles followed by nivolumab 3 mg/kg Q2W)
- Arm B (40 subjects, nivolumab 3 mg/kg + ipilimumab 1 mg/kg every 3 weeks (Q3W) for 4 cycles followed by nivolumab 3 mg/kg Q2W)
- Arm C (40 subjects, Nivolumab (3 mg/kg) Q2W + ipilimumab (1 mg/kg) Q6W)

Subjects to be enrolled in the PC additional cohort will be assigned to one regimen consisting of nivolumab 3 mg/kg Q2W + ipilimumab (1 mg/kg) Q6W + cobimetinib 60 mg orally QD 21 days on/7 days off.

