Tumor Assessment	See Notes	
 • Tumor assessments should occur every 6 weeks (\pm 1 wk) from first dose for the first 24 weeks, then every 12 wks (\pm 1 wk) while on treatment or on treatment hold for any reason until disease progression and treatment discontinuation, whichever occurs later. Additionally, with the exception of crossover participants, tumor assessments will not be required upon initiation of subsequent anti-cancer therapy. • CT chest, CT or MRI abdomen, pelvis and all known sites of disease. Use same imaging method as was used at screening/baseline. • Subjects with a history of brain metastasis should have surveillance MRI approximately every 12 weeks, or sooner if clinically indicated
Clinical Drug Supplies		
IVRS Drug Vial Assignment	X	
Administer Study Treatment	X	See Section 4.5 , Note: Within 3 days from vial allocation, the subject must receive the first dose of study medication. Subjects may be dosed no less than 12 days between doses and no more than 3 days from the scheduled dose.

Table 5.1-3: On-Study Assessments for N-I Arms (Dose Levels 2 and 2b) Week 1-12, Nivolumab + Ipilimumab Combination (CA209032)		
Procedure	Week 1-12, nivolumab and ipilimumab are administered every 3 weeks for 4 doses.	Notes
	Day 1, Week 1, 4, 7, 10	
Safety Assessments		
Targeted Physical Examination	X	Within 72 hours prior to dosing. During treatment hold to be conducted every 12 weeks to adjust to the tumor assessment schedule (see Section 3.1.5).
Vital Signs and Oxygen Saturation	X	Including BP, HR, temperature, and oxygen saturation by pulse oximetry. Pulse oximetry at rest within 72 hours prior to dosing. During treatment hold to be conducted every 12 weeks to adjust to the tumor assessment schedule (see Section 3.1.5).
Physical Measurements (including performance status)	X	Weight and ECOG status The dosing calculations should be based on the body weight. If the subject's weight on the day of dosing differs by > 10% from the weight used to calculate the dose, the dose must be recalculated. All doses should be rounded to the nearest milligram. During treatment hold to be conducted every 12 weeks to adjust to the tumor assessment schedule (see Section 3.1.5).
Adverse Events Assessment	Continuously	eSAEs should be approved in TAO within 5 days from entry
[REDACTED]	[REDACTED]	[REDACTED]

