Laboratory Tests	X	Within 72 hours prior to re-dosing to include CBC w/ differential, LFTs, BUN or serum urea level, creatinine, albumin, Ca, Mg, Na, K, Cl, LDH, glucose, amylase, lipase, TSH (if TSH result abnormal, subsequent testing of Free T4 and Free T3 required). During treatment hold to be conducted every 12 weeks to

Table 5.1-3: On-Study Assessments for N-I Arms (Dose Levels 2 and 2b) Week 1-12, Nivolumab + Ipilimumab Combination (CA209032)		
Procedure	Week 1-12, nivolumab and ipilimumab are administered every 3 weeks for 4 doses.	Notes
	Day 1, Week 1, 4, 7, 10	
		adjust to the tumor assessment schedule (see Section 3.1.5).
Pregnancy Test (WOCBP only)	X	Serum or urine within 24 hours prior to first dose and then every 3 weeks at Week 1-12, then every 4 weeks. During treatment hold to be conducted every 12 weeks and resume per protocol testing once treatment resumes (see Section 3.1.5).
Outcomes Research Assessments		
QoL	X	Collect EQ-5D prior to study drug administration through Week 13, then at the same time of subsequent tumor assessments, during Follow Up 1 and 2 and survival visits. The EQ-5D can be done via a phone contact when a clinic visit is not feasible (ie, follow up scans are being done at another facility or department) in order to not miss the assessment. During treatment hold to be conducted every 12 weeks to adjust to the tumor assessment schedule (see Section 3.1.5).
Pharmacokinetic Assessments		
PK Samples	See Section 5.5.1 for details regarding specific sample timing	
[REDACTED]		
[REDACTED]	[REDACTED]	
[REDACTED]	[REDACTED]	
[REDACTED]	[REDACTED]	

Table 5.1-3: On-Study Assessments for N-I Arms (Dose Levels 2 and 2b) Week 1-12, Nivolumab + Ipilimumab Combination (CA209032)		
Procedure	Week 1-12, nivolumab and ipilimumab are administered every 3 weeks for 4 doses.	Notes
	Day 1, Week 1, 4, 7, 10	
[REDACTED]	[REDACTED]	[REDACTED]
[REDACTED]	[REDACTED]	
[REDACTED]		[REDACTED]
Efficacy Assessment		

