	Day 1 Week 1, 3, 5, 7, 9, etc	
Laboratory Tests	X	Within 72 hours prior to each dose up to and including Week 25 and then every other dose thereafter (Week 29, Week 33, Week 37 etc.). Dosing to include CBC w/ differential, LFTs, BUN or serum urea level, creatinine, albumin, Ca, Mg, Na, K, Cl, LDH, glucose, amylase, lipase, TSH (if TSH result abnormal, subsequent testing of Free T4 and Free T3 required). During treatment hold to be conducted every 12 weeks to adjust to the tumor assessment schedule (see Section 3.1.5).
Pregnancy Test (WOCBP only)	X	Serum or urine within 24 hours prior to first dose and then every 4 weeks. During treatment hold to be conducted every 12 weeks and resume per protocol testing once treatment resumes (see Section 3.1.5).
Outcomes Research Assessments		
QoL	X	Collect EQ-5D prior to study drug administration through Week 13, then at the same time of subsequent tumor assessments, during Follow Up 1 and 2 and survival visits. The EQ-5D can be done via a phone contact when a clinic visit is not feasible (ie., follow up scans are being done at another facility or department) in order to not miss the assessment. During treatment hold to be conducted every 12 weeks to adjust to the tumor assessment schedule (see Section 3.1.5).
Pharmacokinetic Assessments		
PK Samples	See Section 5.5.1 for details regarding specific sample timing	
████████████████████		
████████████████████	████████████████████	

Table 5.1-5: On-Study Assessments for N-I Arms (Dose Level 2c) Nivolumab + Ipilimumab Combination (CA209032)		
Procedure	For Arm N-I Dose level 2c, Nivolumab is administered every 2 weeks, Ipilimumab is administered every 6 weeks	Notes
	Day 1 Week 1, 3, 5, 7, 9, etc specific sample timing	
[REDACTED]	[REDACTED]	
[REDACTED]	[REDACTED]	
[REDACTED]	[REDACTED]	[REDACTED]
[REDACTED]	[REDACTED]	
[REDACTED]		[REDACTED]
Efficacy Assessment		

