Based on SCLC data so far observed in this study with an ORR of about 10% for nivolumab monotherapy and about 23% for the nivolumab + ipilimumab combination therapy, sample sizes of $N = 150$ for nivolumab monotherapy and $N = 100$ for nivolumab + ipilimumab combination therapy (nivolumab 1 mg/kg + ipilimumab 3 mg/kg) will target a Type I error rate of 5% (two-sided) and will have 78% power to detect the difference between these two arms if the true response rates are 10% and 23%, respectively.

Sample Size determination for ovarian cancer cohort

Also in Amendment 09, an ovarian cancer cohort is added and a one stage design with the treatment of 40 subjects for each combination will be used. These sample sizes will provide 79% power to reject the null hypothesis of 10% response rate, if the true response rate is 25% with a two-sided Type I error rate of 5%.

Sample Size determination for the additional pancreatic cancer cohort

A one stage design will be used, with the treatment of 30 subjects with nivolumab 3 mg/kg every 2 weeks, ipilimumab 1 mg/kg every 6 weeks, and cobimetinib 60 mg po qd 21 days on/7 days off. This sample size will provide 70% power to reject the null hypothesis of 10% response rate if the true response rate is 25% with a two-sided Type I error rate of 5%.

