5.7 Outcomes Research Assessments

General health status will be measured using the EQ-5D. The EQ-5D is a standardized instrument for use as a measure of self-reported general health status. The EQ-5D comprises of 5 dimensions (mobility, self-care, usual activities, pain/discomfort, and anxiety) and a visual analog rating scale (VAS). The utility data generated from the EQ-5D is recommended for and commonly used in cost effectiveness analysis.

The EQ-5D measure will be collected as follows:

- Nivolumab monotherapy arm: Collect prior to each study drug administration at Week 1, 3, 5, 7, 9, 11, and 13, then at the same time of subsequent tumor assessments, during Follow Up 1 and 2 and survival visits.
- Nivolumab / Ipilimumab combination arm: Collect prior to each study drug administration at Week 1, 4, 7, 10, and 13, then at the same time of subsequent tumor assessments, during Follow Up 1 and 2 and survival visits.
- The EQ-5D can be done via a phone contact when a clinic visit is not feasible (ie, follow up scans are being done at another facility or department) in order to not miss the assessment.

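### EQ-VAS is to be reported per time point for N and N-I only, but the N-I regimens have different EQ-5D weeks through Week 13, so the ovarian (or any cross-schedule) N-I column changes membership from week to week

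*Protocol*

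**What the plan says.** Section 8.4.6 has the same wording in Revised Protocol 07D and Revised Protocol 08. EQ-VAS at each assessment time point "will be summarized using descriptive statistics by treatment arm (N and N-I), as randomized or assigned". For the five EQ-5D dimensions the next sentence refers to treatment group, without listing the groups, and adds: "Percentages will be based on number subjects assessed at assessment time point".

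The collection rule is the same in every on-study table of Section 5.1: "Collect EQ-5D prior to study drug administration through Week 13, then at the same time of subsequent tumor assessments". What differs is the set of dosing days to which it applies.

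- Table 5.1-3 (Dose Levels 2 and 2b): "Day 1, Week 1, 4, 7, 10", with Week 13 following in Table 5.1-4.
- Table 5.1-5 (Dose Level 2c) and, in 07D, Table 5.1-6 (Dose Level 2d): "Day 1 Week 1, 3, 5, 7, 9, etc".

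Section 5.7, legible only in Revised Protocol 08, gives a single schedule for the combination: "Nivolumab / Ipilimumab combination arm: Collect prior to each study drug administration at Week 1, 4, 7, 10, and 13".

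On numbers, Section 4.4 states: "Subjects to be enrolled in the OC expansion cohort will be randomized in a 1:1:1 ratio to one of 3 dose level groups", with 40 subjects in each of 2, 2b and 2c. For 2d, Section 8.1 of 07D states: "A one stage design will be used, with the treatment of 30 subjects with nivolumab 3 mg/kg every 2 weeks".

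**The concern.** A by-visit summary is read as a curve, and the reader takes a rise or fall as a change in health status. That reading needs roughly the same people at each point. If one N-I column collects regimens that are scheduled in different weeks, part of the movement comes from which regimen is due that week. This is not dropout and would remain under perfect attendance.

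Dose Level 2c was added with tolerability in mind (Section 1.1.9), so a difference in reported health between regimens is one of the things EQ-VAS could show. In a merged column such a difference would appear as week-to-week oscillation.

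**Working it through.** The protocol gives no sample size, power or target for EQ-VAS, so there is no stated figure to reproduce. The check compares visit weeks and counts planned subjects, assuming full attendance.

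**Week sets through Week 13**

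- 3-weekly regimens (2, 2b): {1, 4, 7, 10, 13}
- 2-weekly regimens (2c, 2d): {1, 3, 5, 7, 9, 11, 13}
- In both: {1, 7, 13}
- 3-weekly only: {4, 10}
- 2-weekly only: {3, 5, 9, 11}

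**Ovarian cohort** (Section 4.4: 2 and 2b together 40 + 40 = 80; 2c 40)

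| Week | 2 and 2b | 2c | N-I column | Share on 2c |
|---|---|---|---|---|
| 1 | 80 | 40 | 120 | 33% |
| 3 | 0 | 40 | 40 | 100% |
| 4 | 80 | 0 | 80 | 0% |
| 5 | 0 | 40 | 40 | 100% |
| 7 | 80 | 40 | 120 | 33% |
| 9 | 0 | 40 | 40 | 100% |
| 10 | 80 | 0 | 80 | 0% |
| 11 | 0 | 40 | 40 | 100% |
| 13 | 80 | 40 | 120 | 33% |

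Nobody scheduled at Week 3 is also scheduled at Week 4.

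**Effect on the mean.** Let the mean be m on 2/2b and m + d on 2c at a given week. The N-I column then shows m at Weeks 4 and 10, m + d at Weeks 3, 5, 9 and 11, and (80m + 40(m + d)) / 120 = m + d/3 at Weeks 7 and 13. At Week 1 the assessment is pre-dose and allocation is randomized, so d = 0 in expectation. As an illustration with assumed values, take m = 70 throughout and d between 5 and 10 from Week 3 on. The column reads 70 at Week 1, 75 to 80 at Week 3, 70 at Week 4, 75 to 80 at Week 5 and 71.7 to 73.3 at Week 7, although neither group changes after Week 3. The protocol gives no value for d. If d = 0, the expected curve is flat and only the changing sample remains.

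**If N-I is pooled across tumor types.** On 3-weekly regimens: SCLC expansion 100 + bladder 92 + 105 + ovarian 80 = 377. On 2-weekly regimens: 40 (2c) + 30 (2d) = 70. The column holds 447 at Weeks 1, 7 and 13, 377 at Weeks 4 and 10, and 70 at Weeks 3, 5, 9 and 11. If all four two-stage tumor types also filled to 100 + 70, the 3-weekly count would be 377 + 4 × 170 = 1057 and the shared weeks 1127. The 70 would not change.

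**Where the effect is absent.** In SCLC, gastric, TNBC and bladder every N-I regimen is 3-weekly, so the scheduled set is constant within the tumor type. After Week 13, EQ-5D follows the tumor assessments, which run on one schedule for all regimens.

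**Section 5.7 against Table 5.1-5 (Revised Protocol 08).** Section 5.7 ties collection to drug administration at Weeks 1, 4, 7, 10 and 13, but 2c has no administration at Weeks 4 or 10. Taken literally, 2c is assessed only at Weeks 1, 7 and 13 and the ovarian column is 120, 80, 120, 80, 120. If 2c were assessed at all five weeks regardless of dosing, there would be one schedule and no change of membership. Table 5.1-5 gives neither of these.

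**The case against.** The best reply is that Section 8.4.6 never says the dose levels are combined. It refers to arms as randomized or assigned. Section 3.1 lists each dose level as a treatment arm, and Section 4.4 randomizes ovarian subjects to three named arms. On that reading the parenthesis is shorthand left from the two-arm design, and the analysis plan would split the columns anyway. A by-subject listing of EQ-5D and EQ-VAS is also planned, so results by regimen can be recovered. This shows real ambiguity. It does not remove the fact that the EQ-VAS sentence names two groups, while baseline data, response and survival (Sections 8.4.1 and 8.4.2) are summarized by cohort.

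A reader might also infer more than the text supports:

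- *That the comparison of N with N-I is distorted at most weeks.* The ovarian cohort has no Arm N. Setting N beside 2c/2d subjects only would require pooling across tumor types or merging the pancreatic cohorts. Section 8.4.6 states neither, and this fits poorly with the independent evaluation by tumor type in Section 3.1. No test or contrast of EQ-VAS is planned there.
- *That every N-I curve in the trial is affected.* Four of the six tumor types are not, when taken on their own.
- *That a constant regimen gap would show from Week 1.* Pre-dose assessment and 1:1:1 randomization rule that out in expectation for ovarian.
- *That Section 5.7 makes the problem worse.* It conflicts with Table 5.1-5, but under it Weeks 3, 5, 9 and 11 would drop out for 2c. It is a separate inconsistency.

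**Conclusion.** The point holds in a limited form and is minor. Taken as written, the two-group EQ-VAS summary gives an ovarian N-I column whose planned size moves between 120, 40 and 80 over Weeks 1 to 13, with the 2c share at 33%, 100% or 0%. The same kind of shift arises if N-I is pooled across tumor types, or if the original pancreatic N-I arm is merged with 2d.

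This rests on three things: the literal reading of the parenthesis in Section 8.4.6, the visit weeks of the Section 5.1 tables, and full attendance. The size of any resulting swing in the mean cannot be stated, because it depends on a regimen difference that the protocol does not give.

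The analysis is descriptive, the effect ends after Week 13, and no primary conclusion depends on it. The mismatch between Section 5.7 and Table 5.1-5 for 2c in Revised Protocol 08 stands as a separate, small inconsistency.

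**What to change.** In Section 8.4.6 of both revisions, replace the two-group split with: *by tumor cohort and regimen as randomized or assigned (N and each N-I dose level)*. Use the same grouping for the EQ-5D dimensions. If a pooled N-I summary is wanted, restrict it to Weeks 1, 7 and 13 and the shared tumor-assessment visits. In ovarian this gives 40 scheduled subjects per dose level at each of that level's own weeks, or 120 pooled at Weeks 1, 7 and 13.

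Separately, in Revised Protocol 08, reconcile the EQ-5D weeks in Section 5.7 with the 2-weekly visits for 2c in Table 5.1-5. That revision has no 2d cohort, and its Table 5.1-6 is the follow-up schedule, so nothing needs aligning there for 2d.

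The cost is wording and table layout, with no new data for the summary change. The price is more columns with smaller numbers in each.

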8.5 Interim Analyses

Data will be reviewed during the Dose Escalation Safety Evaluation Phase to determine the maximum tolerated dose level for arm N-I and to make decisions about Stage 2 for each cohort using Simon's 2-stage design. The decision to proceed from Stage 1 to Stage 2 will be conducted for each tumor type and for each treatment arm independently.

An interim analysis may be conducted after Stage 1, by cohort. This interim analysis may be triggered if a "super" response (ie, 8 or more responders out of 18 subjects) is observed or if it is necessary in order to make decisions regarding further development. Summaries and listings of efficacy and safety will be provided. This interim analysis will not impact the study duration and the trial will continue as planned.

Interim analyses may be conducted for supporting internal decision making or for external data disclosure purposes by cohort, depending upon the maturity of the data.

9 STUDY MANAGEMENT

9.1 Compliance

9.1.1 *Compliance with the Protocol and Protocol Revisions*

The study shall be conducted as described in this approved protocol. All revisions to the protocol must be discussed with, and be prepared by, BMS. The investigator should not implement any deviation or change to the protocol without prior review and documented approval/favorable opinion from the IRB/IEC of an amendment, except where necessary to eliminate an immediate hazard(s) to study subjects.

If a deviation or change to a protocol is implemented to eliminate an immediate hazard(s) prior to obtaining IRB/IEC approval/favorable opinion, as soon as possible the deviation or change will be submitted to:

- IRB/IEC for review and approval/favorable opinion
- BMS
- Regulatory Authority(ies), if required by local regulations

Documentation of approval signed by the chairperson or designee of the IRB(s)/IEC(s) must be sent to BMS.

If an amendment substantially alters the study design or increases the potential risk to the subject: (1) the consent form must be revised and submitted to the IRB(s)/IEC(s) for review and approval/favorable opinion; (2) the revised form must be used to obtain consent from subjects currently enrolled in the study if they are affected by the amendment; and (3) the new form must be used to obtain consent from new subjects prior to enrollment.

If the revision is done via an administrative letter, investigators must inform their IRB(s)/IEC(s).

9.1.2 Monitoring

Representatives of BMS must be allowed to visit all study site locations periodically to assess the data quality and study integrity. On site they will review study records and directly compare them with source documents, discuss the conduct of the study with the investigator, and verify that the facilities remain acceptable.

In addition, the study may be evaluated by BMS internal auditors and government inspectors who must be allowed access to CRFs, source documents, other study files, and study facilities. BMS audit reports will be kept confidential.

The investigator must notify BMS promptly of any inspections scheduled by regulatory authorities, and promptly forward copies of inspection reports to BMS.

